6.4.2 Additional analyses

Analysis #1

Goal: To determine if there is a main effect of condition on self-reported PTSD symptoms for meeting PTSD criteria, three weeks after the second experimental session and three weeks after the third experimental session 1.

Population: Intention to treat and Per protocol

Data included in Analyses: PDS Severity Score

Format of analyses: Repeated measures ANOVA

Between-groups Factor: Condition (125 mg MDMA, 25 mg MDMA)

Analysis #2

Goal: To determine if there is a main effect of condition and participation in partial crossover upon PTSD symptoms, meeting PTSD diagnostic criteria, and reduced psychological symptoms three weeks after the third experimental session, and three weeks after the third Stage 2 session.

Population: Intention to Treat, Per Protocol and Partial Crossover

Data included in analyses: CAPS (Global Score and subscales specified above, Diagnostic criteria met, Associated Features), PDS (Severity Score, Rating, Impairment)

Format of Analyses: Repeated measures ANOVA. If multiple scale scores from a single measure are analyzed, Bonferroni corrections will be applied.

Time: Baseline, 3 Weeks after Stage 1 Experimental Session 3, 3 weeks after Stage 2 experimental session 3

Between-groups factors: Condition (125 mg MDMA, 25 mg MDMA)

Analysis #3

Goal: To test for an effect of Stage on PTSD symptoms and meeting criteria for PTSD.

Population: Intention to Treat, Per Protocol and Partial crossover

Data included in analyses: CAPS (Global Score and subscales specified, Diagnostic criteria met, Associated Features), PDS (Severity Score, Rating, Impairment)

Format of Analyses: Repeated measures ANOVA or independent t-tests. If multiple scale scores from a single measure are analyzed, Bonferroni corrections will be applied.

Time: Baseline, 2 months after Stage 1 3rd Experimental Session, 2 months after 3rd Stage 2 Experimental Session

Between-groups factors: Condition (125 m MDMA, 25 mg MDMA)

Analysis #4

Goal: To determine whether there is a continued effect of MDMA-assisted psychotherapy 2, 6 or 12 months after the third experimental session through formal or informal analyses

Population: Extended Assessment 1

Data included in Analysis: CAPS (Global Score, Diagnostic criteria Score, Associated Features), PDS (Severity Score, Rating, Impairment)

Format of Analysis: Informal comparison of descriptive data for the three participants who underwent 2, 6 and 12 month assessment.

Time: Baseline, 2, months after Stage 1 or Stage 2 Experimental Session 3, 6 months after Stage 1 or Stage 2 Experimental Session 3, 12 months after Stage 1 or Stage 2 Experimental Session 3.

Demographic factors analysis

Goal: To test for a main effect of the basic demographic factors gender, age, number of years of psychotherapy and presence of additional affective disorders upon PTSD symptoms across both conditions, meeting PTSD diagnostic criteria, and reduced psychological symptoms and three weeks after 3rd Stage 1 experimental session

Population: Intention to treat, Per protocol

Data included in analysis: CAPS (Global Score and subscales, Diagnostic criteria met, Associated Features) and PDS (Severity Score, Rating, Impairment). Demographic variables will include gender, age, years of psychotherapy, presence of other affective disorder.

Format of analysis: Repeated-measures ANOVA for categorical data (gender, presence of additional affective disorder), linear regression for continuous data (age, years of psychotherapy)

Time: Baseline, End of Stage 1

Between group factors / independent predictors: Gender, age, years of psychotherapy, presence/absence of other affective disorder

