4.0 Study design

The study followed a randomized, active placebo-controlled, double-blind design, with subjects, psychotherapists and independent raters blinded to participant condition. Twelve subjects with treatment-resistant PTSD were randomly assigned after baseline assessment to receive either full dose of 125 mg MDMA followed by a supplemental dose of 62.5 mg MDMA administered 2.5 h

later, or to an active placebo dose of 25 mg MDMA followed by 12.5mg MDMA 2.5h later. Participants underwent three sessions of MDMA-assisted psychotherapy scheduled to occur three to five weeks apart, 1 non-drug-psychotherapy session 24 h after each MDMA-session and 2-4 weekly integrative psychotherapy sessions after each MDMA session. PTSD symptoms were assessed by an independent rater once prior to MDMA-assisted psychotherapy, three weeks after the second MDMA-assisted session, three weeks after the third experimental session. After unblinding, active placebo participants had the opportunity to take part in an open-label continuation of the study, referred to here as "Stage 2." Data gathered three weeks after the third experimental session was treated as the baseline for Stage 2, and outcome measures were administered three weeks after the second and third experimental session. Originally outcome measures would also be given two, six and twelve months after the third experimental session, but the six-month evaluations were discontinued after January 2009 in line with the Amendment 5 of the protocol. Participants receiving the full dose in either Stage 1 or Stage 2 who did not show significant improvement in PTSD symptoms were offered the opportunity to take part in an open-label continuation of the study, "Stage 3", consisting of two additional MDMA sessions. During these sessions, they could receive 125 mg followed 2.5 hours later by 62.5 mg MDMA or a 20% larger dose of 150 mg MDMA, followed by a supplemental dose of 75 mg administered 2.5 hours later, unless contraindicated by safety parameters. Outcome measurements gathered at 2 months after the third experimental session will serve as baseline measures for Stage 3. Stage 3 was also cancelled in line with Amendment 5. Of the 12 participants who completed the study, only three participants underwent Stage 3.

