6.5.2 Subsidiary analyses

Physiological and SUD:

Analysis #1

Goal: To test for the presence of interactions between demographic variables and condition on one or more physiological variable or psychological distress. Performed if and only if there are significant differences in representation of a given demographic variable or feature across conditions (as, more women in one condition than the other), or if doing so gathers essential information on study drug safety.

Population: All enrolled, intention to treat, per protocol, partial crossover

Data included in analyses: Peak SBP, DBP and HR, peak SUD

Format of Analysis: Two-way analysis of variance, one per experimental session in each stage

Between-group factors: Demographic variable (e.g. gender), Condition (125 mg MDMA, 25 mg MDMA).

Analysis #2

Goal: To determine if there is an effect for Stage (e.g. order of administration) upon measures of physiological response or psychological distress taken during full-dose MDMA sessions.

Population: Intention to treat, per protocol [125 MDMA only], partial crossover [previously assigned to 25 mg MDMA]

Data included in analyses: Pre-drug average, peak and post-drug average vital signs computed across all subjects averaged across 1) Randomized or 2) Open label full dose sessions

Format of analysis: Full repeated measures ANOVA

Between group factor: Blinding (Randomized, Open Label)

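### SAP 6.4.2 Analysis #2 crosses Condition with a Stage 2 visit that only the 25 mg arm can reach, so its three-visit condition effect cannot be estimated; Analysis #3 has the same empty cell at its Stage 2 visit

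*SAP*

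**What the plan says.** **Who can have a Stage 2 visit.** SAP 4.0 states: "After unblinding, active placebo participants had the opportunity to take part in an open-label continuation of the study". Protocol 2.1 and 2.8.6 limit Stage 2 in the same way, and SAP 6.5.2 Analysis #2 identifies the crossovers by their original arm: "Population: Intention to treat, per protocol [125 MDMA only], partial crossover [previously assigned to 25 mg MDMA". A full-dose participant with insufficient response can go only to Stage 3 (protocol 2.8.7). The planned allocation is 8 to full dose and 4 to low dose (protocol 2.8.1).

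**Analysis #2 (SAP 6.4.2).** The goal is to look for a "main effect of condition and participation in partial crossover upon PTSD symptoms". The method is a repeated-measures ANOVA with Condition as the only between-groups factor. One time list serves all three populations (intention to treat, per protocol, partial crossover): "Time: Baseline, 3 Weeks after Stage 1 Experimental Session 3, 3 weeks after Stage 2 experimental session 3". Crossover participation is in the goal but is not a factor.

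**Analysis #3 (SAP 6.4.2).** "Goal: To test for an effect of Stage on PTSD symptoms and meeting criteria for PTSD". "Format of Analyses: Repeated measures ANOVA or independent t-tests". "Time: Baseline, 2 months after Stage 1 3rd Experimental Session, 2 months after 3rd Stage 2 Experimental Session". Condition is again the between-groups factor.

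**Related text.** SAP 6.1 says that intention to treat uses whatever data are available. It gives no rule for a visit that one arm cannot have. Protocol 2.8.3 puts its main interest in the interaction of condition with time and expects full dose to be ahead on CAPS two months after the third session. It describes the Stage 2 data as a comparison of scores across stages within Stage 2 participants, probably too few for formal analysis.

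**The concern.** A repeated-measures ANOVA that crosses Condition with Time needs scores from both arms at each listed visit. Here one arm is barred from one visit by design. This is not drop-out, and better follow-up would not repair it.

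As written, the three-visit condition effect in Analysis #2 cannot be produced. The analyst would have to choose later which visits or people to leave out. SAP 8.0 records that preliminary outcome data had already been shown at conferences, so that choice could be made with results known.

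The part of Analysis #2 that works is worth protecting. It is the only unconditional test of Condition, at three weeks after Stage 1 session 3, on CAPS Associated Features, PDS Rating and PDS Impairment. Section 6.4.1 covers CAPS Global, subscales and diagnosis, and Analysis #1 covers PDS Severity only.

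**Working it through.** The documents give no figure to reproduce for this point, so the check is whether each contrast can be estimated.

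**Inputs.** 8 at 125 mg and 4 at 25 mg (protocol 2.8.1). The number of crossovers, k, is not given, so k = 0 to 4. T2 is three weeks, and T3 two months, after Stage 1 session 3 (protocol 2.8.2).

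**Analysis #2: participants per cell**

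| | Baseline | T2 | Stage 2 visit |
|---|---|---|---|
| 125 mg | 8 | 8 | 0 |
| 25 mg | 4 | 4 | k |

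**Condition-by-Time model** (assumed; the SAP does not state the interaction). With one mean per cell, a contrast is estimable only if adding it to the design matrix leaves the rank unchanged, so it may put no weight on an empty cell. The rank is the number of filled cells: 4 of 6 for k = 0, and 5 of 6 for k = 1 to 4.

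| Contrast | Estimable? |
|---|---|
| Condition averaged over three visits (weight 1/3 on the empty cell) | No, any k |
| Condition at the Stage 2 visit | No, any k |
| Baseline-to-Stage 2 change, by Condition | No, any k |
| Condition at T2, or averaged over baseline and T2 | Yes, any k |
| Baseline-to-T2 change, by Condition | Yes, any k |
| T2-to-Stage 2 change within crossovers | Yes, k ≥ 1 |

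**Complete cases only** (assumed). 0 of 8 at 125 mg and k of 4 at 25 mg remain. With an intercept, Condition and two time terms, the rank is 3 of 4, so Condition drops out.

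**Additive model on all rows** (no interaction, k = 1 to 4). The rank is 4 of 4, and a condition coefficient is returned:

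0.5 × (baseline difference) + 0.5 × (T2 difference) + 0 × (Stage 2 scores).

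The weights are the same for within-person correlations of 0, 0.3, 0.5 and 0.7 (assumed range). With equal baselines and a T2 difference D, it reports 0.5D. The output looks like a three-visit effect but contains nothing from Stage 2.

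**Analysis #3.** The third visit is again empty for 125 mg.
- The three-visit condition effect in the ANOVA is not estimable.
- A t-test of Condition at the Stage 2 visit would compare 0 with k people.
- Condition at T3 is estimable if at least one 25 mg participant has that visit. Protocol 2.8.2 limits T4 and T5, but not T3, to low-dose participants who decline Stage 2, so even crossovers may have it.
- A cross-visit contrast (125 mg after Stage 1 against former 25 mg after Stage 2) is estimable for k ≥ 1, with 8 + k − 2 degrees of freedom, at most 10.

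**Is a crossover's T3 score still a Stage 1 score?** Count weeks from Stage 1 session 3. T2 is week 3, and T3 is 2 × 365.25/12/7 = week 8.7. Assume the preparatory visit falls at T2. The first Stage 2 session, one or two weeks after it (protocol 2.8.6), is then in week 4 or 5. The documents give session spacings of both two to four and three to five weeks, which need reconciling, so 2 to 5 is used.

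| First session | Spacing 2 | 3 | 4 | 5 |
|---|---|---|---|---|
| Week 4: sessions before week 8.7 | 3 | 2 | 2 | 1 |
| Week 5: sessions before week 8.7 | 2 | 2 | 1 | 1 |

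With a prompt start, a crossover has had 1 to 3 open-label sessions by T3. The count is 0 only if Stage 2 dosing starts more than 8.7 − 3 = 5.7 weeks after T2.

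**Testing within crossovers.** If a signed-rank test were used, its smallest two-sided p is 2/2^4 = 0.125 with four people.

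**The case against.** **The time list may be a union.** Analysis #2 names two effects and three populations. One could read it as Condition at shared visits in the randomised sets, and Stage 2 within the crossovers. That would be sensible, but the text gives one time list and one Condition factor for all three populations, and the partial crossover set contains only one level of Condition.

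**All available data will be used.** This answers the complete-case problem, but using every row does not fill an empty cell.

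**The interaction is borrowed.** This is fair. The protocol 2.8.3 sentence concerns the treatment-versus-control time course, and the SAP is silent. The additive alternative gives Stage 2 no weight.

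**Counts may differ.** Protocol 2.7 replaces drop-outs, and intention to treat keeps anyone with one session, so the numbers could exceed 8 and 4. The empty cell does not depend on them.

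**Stronger readings a reader might infer.**
- *That the t-test option makes Analysis #3 safe.* It does so only for a cross-visit contrast that the SAP never states. SAP 6.5.2 does speak of an "effect for Stage (e.g. order of administration"), but for vital signs and distress, with Blinding as the factor. For CAPS and PDS, protocol 2.8.3 compares stages within person.
- *That the ANOVA in Analysis #3 cannot compare conditions and should go.* Condition at T3 is estimable if any 25 mg participant has the visit. Protocol 2.8.3 names that comparison and no other SAP analysis tests it: 6.4.1 stops at T2, and Analysis #4 is informal with no Condition factor.
- *That the main result is at risk.* Section 6.4.1 uses Stage 1 visits only.

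It also stands that the protocol already expected too few Stage 2 participants for formal analysis.

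**Conclusion.** The concern holds for Analysis #2 and for the Stage 2 level of Analysis #3. The empty cell follows from the eligibility rule alone and needs no assumption. The loss of the three-visit condition effect for every k rests on a Condition-by-Time model. The loss of all eight 125 mg participants rests on complete-case handling. The warning about crossovers' T3 scores rests partly on the rule that breaks each participant's blind at T2 (protocol 2.8.6) and partly on an assumed prompt start to Stage 2.

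What is lost is limited to contrasts that involve 125 mg at a Stage 2 visit. Only secondary analyses are affected. This should be fixed because a prespecified analysis fails as written, but it does not threaten the primary comparison.

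**What to change.** **Analysis #2.** Limit the Condition test to baseline and T2 (Condition by Time, 1 and 12 − 2 = 10 df at 8 against 4). Apply it to CAPS Associated Features, PDS Rating and PDS Impairment. The other scores are already tested in 6.4.1 or Analysis #1, and repeating them would give the primary outcome a second Condition p-value. Report Stage 2 separately within the Partial Crossover set, with T2 as baseline as protocol 2.8.2 provides. Keep this mainly descriptive. Protocol 2.8.3 does plan some nonparametric testing that includes open-label final sessions, so a test is not barred, but label it exploratory.

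**Analysis #3.** Remove the Stage 2 level from the Condition-by-Time model. Keep Condition at baseline and two months after Stage 1. State that 25 mg crossovers are unblinded at T2 and may have begun open-label dosing by then, and show the result with and without their post-T2 scores. If all four cross over, the second version has no 25 mg scores, and the report should say so. Define the Stage effect separately as Stage 2 against Stage 1 within crossovers, naming the Stage 1 score used; T2 is the last one before unblinding. If the cross-visit group contrast is also reported, label it non-randomised and confounded with order.

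**Cost.** SAP wording only. The Condition contrast at the Stage 2 visit is given up, and it could not be estimated anyway. The two-month Condition comparison is kept, with its caveat. Any cross-visit contrast has at most four people on one side under the planned allocation.

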2.6. Questions and Hypotheses

The following main questions are to be explored in the proposed study:

1. Can MDMA, in the doses to be used in this study, be safely administered in the population of treatment-resistant PTSD patients without any serious adverse events?
2. Will patients receiving the larger, fully active dose of MDMA, in combination with non-drug assisted psychotherapy, demonstrate greater symptomatic improvement than patients given an active placebo dose of MDMA in combination with non-drug psychotherapy?
3. Will patients receiving three MDMA sessions in combination with non-drug psychotherapy demonstrate an additional improvement compared to patients receiving only two sessions?
4. Can treatment effects of MDMA-assisted psychotherapy be maintained beyond end of treatment?

Based on the reviewed research, the following hypotheses were formulated:

Re 1. PTSD patients receiving the fully active dose of MDMA will not experience any serious adverse events. The supplemental dose of MDMA will be tolerated both in the low and fully active dose conditions.

Re 2. There will be trends for people receiving the fully-active dose of MDMA to demonstrate greater symptomatic improvement after receiving MDMA-assisted therapy than people receiving the low dose of MDMA, including greater reduction in symptom severity and intensity, and overall improvement in PTSD symptoms, as measured via the CAPS and PDS, with CAPS score serving as the primary outcome measure.

Re 3. 3 experimental MDMA-assisted sessions will lead to better results compared to only 2 experimental MDMA-assisted sessions, as measured via the CAPS and PDS, with CAPS score serving as the primary outcome measure.

Re 4. The treatment gains will remain stable at the 2, 6 and 12 months assessments.

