3.0 Study Objectives

As stated in the protocol, the following main questions are to be explored in the proposed study:

1. Can MDMA, in the doses to be used in this study, be safely administered in the population of treatment-resistant PTSD patients without any serious adverse events?
2. Will patients receiving the larger, fully active dose of MDMA, in combination with non-drug assisted psychotherapy, demonstrate greater symptomatic improvement than patients given an active placebo dose of MDMA in combination with non-drug psychotherapy?
3. Will patients receiving three MDMA sessions in combination with non-drug psychotherapy demonstrate an additional improvement compared to patients receiving only two sessions?
4. Can treatment effects of MDMA-assisted psychotherapy be maintained beyond end of treatment?

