3.2 Secondary Objectives

- To evaluate changes in PTSD symptoms as assessed via PDS at baseline, the day after each experimental session, and three weeks after the third experimental session.
- To evaluate PTSD symptoms measured by CAPS and PDS scores three weeks after the second Stage 2 experimental session, three weeks after the third Stage 2 experimental session and two months after the third Stage 2 experimental session.
- To formally or informally evaluate CAPS scores in participants who underwent an optional open label continuation for treatment non-responders (Stage 3).
- To evaluate changes in PTSD symptoms assessed via CAPS and PDS scores obtained two, six and twelve months after the third experimental session.

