6.0 Analyses

6.1 Study population

See protocol. All participants were diagnosed with chronic PTSD, met DSM IV criteria, and had Global CAPS scores of 50 or greater upon enrollment. They had either undergone psychotherapy, pharmacotherapy or both without a significant reduction in PTSD symptoms.

All clinical data will be presented in tabular listings. All analyses will be carried out with SPSS of Version 12.0 or higher.

Definitions of subject populations for analysis:

All Enrolled: All participants who signed an informed consent form and completed baseline measures.

Intention to treat: All participants who were randomized to a condition and underwent at least one experimental session. All available data will be used.

Per Protocol: All participants who completed Stage 1 and underwent assessment of PTSD symptoms two months after the second experimental session. Analyses may be conducted with and without a participant who corresponds to a major protocol deviation.

Partial crossover: All participants who completed Stage 2 as well as Stage 1.

Extended Assessment 1: All participants who underwent assessment two, six and twelve months after their third Stage 1 or Stage 2 experimental session.

Extended Assessment 2: All participants who underwent Stage 3

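### SAP Analysis #4, the only analysis aimed at a continued effect, is limited to three people seen at all of 2, 6 and 12 months and has no end-of-treatment score to compare with

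*SAP*

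**What the plan says.** **The question.** SAP section 3.0, question 4, asks: "Can treatment effects of MDMA-assisted psychotherapy be maintained beyond end of treatment". Protocol section 2.6 turns this into a hypothesis: "The treatment gains will remain stable at the 2, 6 and 12 months assessments". SAP section 3.2 adds a secondary objective, with no condition that a person attend every visit: "To evaluate changes in PTSD symptoms assessed via CAPS and PDS scores obtained two, six and twelve months after the third experimental session".

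**The analysis.** The goal of Analysis #4 in SAP section 6.4.2 is "To determine whether there is a continued effect of MDMA-assisted psychotherapy 2, 6 or 12 months after the third experimental session", by formal or informal means. Its population is defined in SAP section 6.1: "Extended Assessment 1: All participants who underwent assessment two, six and twelve months after their third Stage 1 or Stage 2 experimental session". Its format is "Informal comparison of descriptive data for the three participants who underwent 2, 6 and 12 month assessment". Its time row begins "Time: Baseline, 2, months after Stage 1 or Stage 2 Experimental Session 3" and goes on to the 6- and 12-month visits.

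**The visits.** SAP section 4.0 states that "the six-month evaluations were discontinued after January 2009 in line with the Amendment 5 of the protocol". Protocol section 2.8.2 names the assessment 3 weeks after session 3 (T2) as end of treatment, and calls the 2-, 6- and 12-month visits (T3 to T5) follow-up.

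**The concern.** Two features of Analysis #4 do not match the question it serves.

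First, the goal is met by a score at 2, 6 *or* 12 months, but the population and format require 2, 6 *and* 12 months. Membership therefore depends on a visit that was withdrawn partway through the study. Followed as written, the analysis leaves out anyone with 2- or 12-month scores who was never due a 6-month visit.

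Second, maintenance beyond end of treatment is a comparison of follow-up with end of treatment. The time row offers only baseline as a pre-follow-up reference. A difference from baseline can show that some effect is still present. It cannot show whether the gain reached at end of treatment was kept. At stake is whether the report can answer one of the study's four main questions.

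**Working it through.** No sample-size or power figure is attached to this point. The count of three is a tally that nothing in the documents can regenerate, so the check is mainly textual.

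**Step 1: population.** The goal reads *or*; the definition of Extended Assessment 1 and the format read *and*. SAP section 4.0 gives 12 completers. Share analysed = 3/12 = 25%, so 12 − 3 = 9 people fall outside, whatever follow-up scores they have. How many of the 9 have a 12-month score is not stated; the possible range is 0 to 9.

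**Step 2: reference score.** Each SAP efficacy analysis was checked for an end-of-treatment score (3 weeks after session 3) and for a later follow-up score.

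| SAP analysis | End-of-treatment score | Follow-up score |
|---|---|---|
| Main (6.4.1) | yes | none |
| Additional #1, PDS | yes (from its goal) | none |
| Additional #2 | yes | none |
| Additional #3, effect of Stage | no | 2 months |
| Additional #4 | no | 2, 6, 12 months |
| Demographic factors | yes | none |
| Subsidiary (6.4.3) | yes | none |

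No row has both, so no SAP analysis compares follow-up with end of treatment.

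**Step 3: could baseline serve as that reference for Stage 2 participants?** SAP section 4.0 makes their Stage 1 score, 3 weeks after session 3, the Stage 2 baseline. That score precedes their full-dose sessions, so it is not an end-of-treatment score for that course.

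**Step 4: what a baseline reference hides.** Hypothetical CAPS scores: 70 at baseline, 40 at T2, 55 at 12 months. Change from baseline at 12 months = 70 − 55 = 15 points, which reads as a continued effect. Gain at T2 = 70 − 40 = 30 points. Loss since T2 = 55 − 40 = 15 points, and 15/30 = half of the gain. Analysis #4 reports the first figure and not the last. Any loss between T2 and the 2-month visit, an interval of about 8.7 − 3 = 5.7 weeks, is likewise not summarised by any SAP analysis.

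**Step 5: precision if the set is widened (scale only).** The 95% half-width of a mean change, in SD units, is t(0.975, n−1)/√n.

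| n | Half-width |
|---|---|
| 3 | 2.48 SD |
| 5 | 1.24 SD |
| 9 | 0.77 SD |
| 12 | 0.64 SD |

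These show what the proposed interval could deliver at each possible n. They do not measure a fault in the stated format, which plans no interval and no test. If the goal's formal option were taken with the signed-rank test of protocol section 2.8.3, the smallest two-sided exact p would be 2/2³ = 0.25 at n = 3, and at least 6 pairs would be needed to go below 0.05 (2/2⁶ = 0.031).

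**The case against.** The strongest reply is that nothing is lost. SAP section 6.1 puts all clinical data into tabular listings, which section 1.0 defines as per subject, and the section 6.4 summary tables carry no visit restriction. Protocol section 2.8.3 plans a CAPS time-course graph for each patient, and a comparison of baseline with 2 months after each participant's final session that needs no 6-month visit. With 12 people, a reader could see the change from T2 in the listings. Analysis #4 is also informal and secondary, and a baseline reference does fit the words of its goal. The three may simply be those who were followed that far: Amendment 5 and the SAP's attached time-and-events table, which might explain the count, were not among the documents available.

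Much of this stands, and it rules out several stronger readings that a reader might infer:

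- *That follow-up would be visible only for the three.* The listings contradict this.
- *That nine people's 12-month scores are discarded.* No text shows that any of the nine has one.
- *That a test is planned which cannot reach significance.* The stated format is descriptive.
- *That the three are the same people as the three who entered Stage 3.* The documents give both counts and do not link them.

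What does not stand is that the question is therefore answered. A listing is not a summary of change. The protocol's graphs are not carried into the SAP, and its 2-month comparison also starts from baseline. Question 4 and hypothesis 4 concern gains kept after treatment, and no SAP analysis reports that.

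**Conclusion.** The point holds in two parts. The population of Analysis #4 contradicts its own goal by requiring a discontinued visit. Its time row omits the end-of-treatment score, so the SAP contains no summary of change from end of treatment to follow-up. The second part holds whatever the number followed. The first is bounded: 3 of 12 completers are analysed, and between 0 and 9 more could enter at a given visit, possibly none at 12 months.

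This should be fixed, since a stated main question otherwise has no matching analysis and the remedy is cheap. It does not touch the primary objective or the main analysis. Confidence is moderate, because the number of scores at each follow-up visit is not given and the amendment text was not available. The conclusion assumes that T2 in protocol section 2.8.2 is the end of treatment meant by question 4.

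**What to change.** - **Set.** Include everyone with an end-of-treatment score and one or more later follow-up scores after session 3 of their last Stage 1 or Stage 2 course. Do not require the 6-month visit.
- **Reference.** Add the score 3 weeks after that session 3 to the time row.
- **Report.** At each follow-up visit give n and the change in CAPS and PDS from end of treatment and from study baseline, descriptively, with a 95% interval. For Stage 2 participants, state the Stage 2 baseline as well.
- **Separate and flag.** Show low-dose participants who declined Stage 2 separately. Identify scores taken after Stage 3 sessions; dropping those people would remove participants selected for insufficient response and flatter durability. Flag later psychotropic drugs or psychotherapy only where already recorded: protocol section 2.7.1 says the 6- and 12-month visits go ahead regardless of new treatment, but not that such treatment is recorded.
- **Interpretation.** State that a non-significant change is not proof of stability. Label the revision post hoc, because SAP section 8.0 says outcome data were presented in 2010 and 2011.

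The cost is revised SAP wording and slightly more tabulation of scheduled scores, with no new visits. The downside is that the table may show no added participants at 12 months.
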